Drug use. During TLFB interviews, participants indicated whether they used any of 10 different drug types. Responses produced two count variables indicating the number of days participants used cannabis and the number of days they reported the use of any illicit drugs, including: cocaine, crack, methamphetamine, ecstasy, ketamine, GHB, and psychedelics. Self-reported drug use was corroborated by fingernail assay. See supplemental material for details.

Current PrEP uptake was assessed using a single survey item, "Have you ever been prescribed PrEP (HIV pre-exposure prophylaxis)?" Participants taking PrEP reported days they missed their PrEP on the TLFB interview. Responses were used to create a dichotomous variable indicating whether or not participants took PrEP on at least 57% of days (corresponding to at least 4 days out of 7 on average). Self-reported PrEP adherence was corroborated with DBS results. See supplemental material for details.

Sexual HIV TRB. During TLFB interviews, participants indicated days they had (insertive or receptive) anal sex with any casual partners and whether a condom was used. Responses were aggregated to create a variable indicating the number of times the participant had CAS with a casual partner. If participants were prescribed PrEP and reported missing 13 doses or fewer, they were assigned a value of 0, reflecting that the use of PrEP on at least 4 of 7 days is sufficient to achieve reductions in HIV TRB (28). Self-reported CAS with casual partners was corroborated by bacterial STI diagnosis. See supplemental material for details.

Putative moderators

Relationship satisfaction was assessed using the approximation to ideal subscale of Kurdek's (29, 30) Multiple Determinants of Relationship Commitment Inventory (MDRCI). The subscale consists of 4 items (e.g., "My current relationship comes close to matching what I would consider to be my ideal relationship"). Response options ranged from 1 (strongly disagree) to 5 (strongly agree). Total score reliability was good (Cronbach's $\alpha = .848$).

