Several considerations led to the inclusion of model covariates. Consistent with guidance for the analysis of data from randomized controlled trials that utilize stratified randomization (16), stratification variables were included as covariates in regressions predicting latent growth factors. The COVID-19 pandemic and recovery corresponded with changes in substance use and sexual behavior among SMM. To account for this, models incorporated a dichotomous, timevarying predictor indicating whether an assessment occurred before or after March 2020. All models were calculated using full-information maximum likelihood estimation in Mplus Version 8.0. This permitted the retention of all randomized cases consistent with the intent-to-treat paradigm. Model significance was evaluated using a robust log-likelihood $\chi 2$ test comparing the log-likelihood of the specified model to a null-model – in which all structural coefficients associated with the regression of latent growth factors on condition and site were constrained to be zero. Where model results were significant, the effect of the PARTNER intervention was evaluated by examination of regression parameters for Slopes 1 and 2. Given the directional nature of hypotheses, single-sided p-values were used to determine the

significance of the intervention effect. When evaluating the significance of putative moderators and associated interaction terms, two-sided p-values were used.

Power analyses

We utilized the *Test for the Ratio of Two Negative Binomial Rates* module in PASS 19 to evaluate power to detect between-condition differences in drug use frequency at any one follow-up time point. Power (1-beta) was set to .80 and the probability of type II error (alpha) was set to .05. The number of exposures was set to 30 (the number of days of use assessed in the TLFB). The rate of use in the education condition was set to 3, 6, and 9. Meanwhile dispersion values of 1, 2, and 4 were tested. Power was highest at low levels of dispersion and high based rates of use in the education condition. Under these circumstances, the study has power=.80 to detect a rate ratio of 0.70 or a 30% reduction in drug use instances. At high levels of dispersion and low base rates, the study would be expected to detect a rate ratio of 0.48.

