Power to detect differences in HIV transmission risk behavior was calculated in 2 ways. First, using procedures similar to those described for drug use, the study has power to detect a rate ratio between 0.48 and 0.69 in the number of CAS events in the absence of PrEP. This calculation tested average rates of CAS in the absence of PrEP in the education condition of 1, 3, and 5 instances and dispersion was tested at values of 1, 2, and 4. Power to detect significant differences in the odds of a positive STI test was calculated using the *inequality tests for 2 proportions in a repeated measures design* module [60]. Analyses specified 4 waves of data, power (1-beta) was set to .80, and the probability of type II error (alpha) was set to .05. Autocorrelation (rho) was permitted to vary between .25 and .75. The proportion of positive STI diagnosis in the education condition was tested at values of .13, .10, and .07. Power declined as rho increased. Power increased with the proportion of positive diagnoses in the education condition. Analyses suggested that the study is adequately powered to detect large effects, associated with an odds ratio between 0.20 (under the least favorable conditions) and 0.32 (under the most favorable).

Power to detect differences in PrEP uptake was similarly calculated using the *inequality tests for 2* proportions in a repeated measures design module [60]. Analyses specified 4 waves of data, power (1-beta) was set to .80, and the probability of type II error (alpha) was set to .05. Autocorrelation (rho) was permitted to vary between .25 and .75. We estimated that on average 35% of the education condition would be on PrEP during the follow-up period. The proposed sample is sufficient to detect an odds ratio

of 1.90 even at the highest values of rho, which corresponds to approximately 51% of the PARTNER condition initiating PrEP. With regard to adherence, assuming approximately 100 participants (45% of the sample assuming 80% retention) are on PrEP at any follow-up point and 75% of the control condition is adherent to their PrEP medication (Cronbach alpha=.05; and ρ =.25 to .50), results suggested that the study has power=.80 to detect an odds ratio of approximately 3.0.

Equivalency Checks

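### The negative binomial power inputs count the 30-day window twice, so the detectable ratios for drug use, and apparently for CAS, rest on wrong control means

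*Combined protocol and SAP*

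**What the plan says.** The Power analyses section uses the negative binomial rate-ratio module of PASS to assess "power to detect between-condition differences in drug use frequency at any one follow-up time point". Power is .80 and alpha .05 (the text labels alpha as type II error; I take it as type I). The other drug-use inputs are:

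- exposure: "The number of exposures was set to 30 (the number of days of use assessed in the TLFB";
- control rate: "The rate of use in the education condition was set to 3, 6, and 9", with no time unit;
- dispersion: 1, 2 and 4.

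The stated detectable ratios are 0.70 (low dispersion, high base rate) and 0.48 (high dispersion, low base rate).

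The CAS calculation is described as following a procedure like the one for drug use: "This calculation tested average rates of CAS in the absence of PrEP in the education condition of 1, 3, and 5 instances", with the same dispersions. No separate exposure is given. The result is that "the study has power to detect a rate ratio between 0.48 and 0.69 in the number of CAS events in the absence of PrEP".

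Under Primary outcomes, drug use is counted in days: "Responses produced two count variables indicating the number of days participants used cannabis", with a second such count for other illicit drugs. Sexual TRB is a number of CAS occasions with casual partners.

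**The concern.** Exposure and rate must be in matching units. If exposure is 30 days, the rate has to be per day. Control rates of 3, 6 and 9 per day cannot describe a days-of-use variable, which takes at most one count per day. They are sensible only as totals for the whole window, and then the exposure should be 1.

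Drug use and TRB are primary outcomes, and these four ratios are the plan's only statement of the count effects it can detect. An inflated exposure makes the sampling variation of the counts almost vanish from the variance. The calculation then depends on dispersion alone and looks more precise than it is at a given n and sidedness.

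**Working it through.** **Window.** The power section gives 30 TLFB days. The TRB rule agrees: "If participants were prescribed PrEP and reported missing 13 doses or fewer, they were assigned a value of 0", and (30 − 13)/30 = .567, which matches the adherence threshold, "whether or not participants took PrEP on at least 57% of days".

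**Implied control means (rate × exposure).** Drug use: 3×30 = 90, 6×30 = 180, 9×30 = 270 use-days. CAS: 1×30 = 30, 3×30 = 90, 5×30 = 150 events. Over the nine rate-by-dispersion combinations for drug use, a negative binomial with these means puts 41-89% of control participants above 30 use-days. With exposure 1 the share is 0-9%.

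**Formula.** With n per arm, exposure T, rates r0 and r1 = RR·r0, and dispersion k (variance μ + kμ²):

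V1 = (1/T)(1/r0 + 1/r1) + 2k

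power = Φ{[√n·|ln RR| − z_α·√V0]/√V1}

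The plan does not name the null variance V0. I used two options: unpooled (V0 = V1) and control-rate (V0 = 2/(T·r0) + 2k). Ranges below run across the two. The cases are drug use (r0 = 9, k = 1) and (3, 4), and CAS (5, 1) and (1, 4). The text supports this pairing for drug use; for CAS I assume it.

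**Reproducing the plan's figure.** Drug use, r0 = 9, k = 1, T = 30, n = 120, two-sided, unpooled, at RR = .696: V1 = (1/30)(.111 + .160) + 2 = 2.009. SE = √(2.009/120) = .1294. RR = exp(−2.802 × .1294) = .696, against 0.70 stated.

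**Changing only the exposure.** With T = 1, at RR = .680: V1 = .111 + .163 + 2 = 2.274. SE = .1377. RR = exp(−2.802 × .1377) = .680.

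Detectable ratios at power .80:

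| Setting | Drug 9, k=1 | Drug 3, k=4 | CAS 5, k=1 | CAS 1, k=4 |
|---|---|---|---|---|
| Stated | 0.70 | 0.48 | 0.69 | 0.48 |
| T=30, 120/arm two-sided | .696 | .484-.485 | .695-.696 | .483 |
| T=30, 96/arm one-sided | .698 | .487 | .697-.698 | .486 |
| T=1, 120/arm two-sided | 0.68 | 0.46-0.47 | 0.67 | 0.42-0.44 |
| T=1, 96/arm one-sided | 0.68 | 0.47 | 0.67 | 0.43-0.44 |
| T=1, 120/arm one-sided | 0.71 | 0.51 | 0.70 | 0.47-0.48 |

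Power at the stated ratios:

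| Setting | Drug 0.70 | Drug 0.48 | CAS 0.69 | CAS 0.48 |
|---|---|---|---|---|
| T=30, either setting above | .79 | .81 | .82 | .81 |
| T=1, 120/arm two-sided | .737-.743 | .763-.775 | .731-.743 | .675-.710 |
| T=1, 96/arm one-sided | .750-.756 | .773-.783 | .745-.755 | .697-.725 |
| T=1, 120/arm one-sided | .829-.833 | .849-.856 | .824-.832 | .779-.803 |

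**Which exposure was used?** Over n = 70 to 180 per arm, one- or two-sided, the smallest achievable maximum error across the four ratios is about .005 with T = 30 (119 per arm two-sided, 94 one-sided). With T = 1 it is .019 (unpooled) or .015 (control-rate).

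Two further signs point to T = 30. The worst case is 0.48 for both drug use (rate 3) and CAS (rate 1). That is expected at T = 30, where the rate term is negligible (.484 against .483, unpooled), whereas at T = 1 and 120 per arm two-sided the two separate (.463 against .422). Also, at T = 30 and k = 1, moving the drug-use base rate from 3 to 9 changes the detectable ratio only from .695 to .696 (120 per arm two-sided). At T = 1 it goes from .650 to .680. The range of base rates therefore tested almost nothing.

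**The case against.** **CAS is not capped.** It is a count of events, so 30 to 150 in 30 days is implausible, not impossible. The CAS exposure is also inferred, from the cross-reference to the drug-use procedure and from the numerical fit. This stands, and the word impossible applies only to drug-use days.

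**Rates may be per day.** The hypotheses and the power text speak of use instances, so the rates could be read as instances per day. The calculation would then be for a different variable from the days-of-use outcome under Primary outcomes, so this reading does not rescue it.

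**The software run is not shown.** True. The fit to exposure 30 supports the reading of the text but is not proof by itself.

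**The effect is modest and may vanish.** At fixed n and sidedness the drug-use ratios move by about .01 to .02. The Detailed analytic plan tests the intervention effect one-sided and retains all randomised cases. With 240 participants allocated equally, three stated ratios then keep .82-.86 power and the fourth has .78-.80. This stands.

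**A reader could supply the missing inputs.** Partly true: N = 240, equal allocation and one-sided testing are in the document, and 80% retention (96 per arm) appears, for PrEP adherence only. What is missing is which combination this calculation used.

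**It is late.** The document is dated January 2024 and reports follow-up results in the past tense. A rerun cannot change the sample size; it corrects the record.

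**Conclusion.** The input error is real. For drug use, exposure 30 with control rates of 3, 6 and 9 contradicts the outcome definition. For CAS the same error is probable.

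Its size depends on settings the section does not declare. In the two settings that come close to the published ratios, the correction takes power at those ratios below .80: about .74-.78 for drug use and .68-.76 for CAS. Low-rate, high-dispersion CAS is hit hardest, from 0.48 to 0.42-0.44.

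A reader might infer three stronger things that the documents do not support:

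- **That the stated ratios are always too favourable.** They are not: with a one-sided test and all 120 per arm they are essentially met.
- **That the low-rate CAS ratio needs more participants than were enrolled.** The one-sided requirement is 128 per arm with unpooled variance but 119 with control-rate variance, so the conclusion turns on an unstated formula choice.
- **That the primary analysis is underpowered.** The calculation concerns a single follow-up time point and says nothing about the piecewise growth model.

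The assumptions are the variance formula above, alpha .05 read as type I error, and the pairing of best and worst CAS cases with rate and dispersion.

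**What to change.** Rerun both negative binomial calculations with exposure 1, or equivalently with daily rates (3/30, 6/30, 9/30 for drug use; 1/30, 3/30, 5/30 for CAS) and exposure 30. State the rate unit, the sidedness (matching the one-sided test in the Detailed analytic plan), the analysed n per arm and the null-variance option. State the CAS exposure explicitly.

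Possible text, with the figures to be confirmed by the rerun: *Control means were 3, 6 and 9 use-days (CAS: 1, 3 and 5 events) per 30-day window; dispersion 1, 2 and 4; one-sided alpha .05; power .80; null variance [option]. Detectable rate ratios range from about 0.71 to 0.51 (drug use) and 0.70 to 0.47-0.48 (CAS) if 120 per arm contribute, and from about 0.68 to 0.47 and 0.67 to 0.43-0.44 if 96 per arm contribute.*

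The 96 per arm is an assumption: it carries the 80% retention of the adherence calculation over to these outcomes.

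The cost is one rewritten power passage. No new data, no new model and no change to trial conduct are needed, and the ratios may move slightly in either direction depending on the settings declared.
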